## **9.3 Data Analyses Plans**

Primary outcome variable: The difference in SUVmax, SUVpeak and proliferative tumor volume between baseline and 2 cycles of chemotherapy will be correlated with overall survival at 1 and 2 years and with progression free survival at 6 months and at 1 year.

The primary outcome of the study is to establish which degree of change in the PET/CT quantitative parameters can predict patients overall survival and progression free survival. The SUVmax (representing the single voxel with the highest activity concentration), SUV peak (which is defined as the average SUV within a 1 cubic cm volume within the region of the tumor with the highest metabolic activity) and proliferative tumor volume of the pancreatic tumor will be measured.

Univariate and multiple cox regression model are going to be used. P-value less than 0.05 will be considered as statistical significant.

Secondary outcome variable: the difference in SUVmax, SUVpeak and proliferative tumor volume between baseline and 2 cycles of chemotherapy will be correlated with binary tumor outcome measured from MRI/CT (resectable versus non-resectable disease) at 6 month using logistic regression. A multiple logistic regression with stepwise selection algorithm will be used to select the most correlated variable(s). Areas under the ROC curve (AUC) and corresponding 95% confidence interval will be calculated for all models. Leave one out cross validation will be applied to avoid over-fit.

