**STUDY SUMMARY**

Title	Initial evaluation of role of early interim F-FLT PET/CT for outcome prediction in pancreatic adenocarcinoma
Short Title	FLT PET/CT and Pancreatic cancer early therapy assessment
Protocol Number	Version 7
Phase	Clinical study phase (e.g., Phase II)
Methodology	Prospective cohort study
Study Duration	2 years
Study Center(s)	UT Southwestern Medical Center - Single-center
Objectives	
 
• To assess if percentage change in F-FLT PET/CT quantitative parameters (SUV max, or SUV peak or proliferative tumor volume) after 2 cycles of neoadjuvant chemotherapy can predict overall survival at 1 and 2 years and progression free survival at 6 months and 1 year in patients with resectable, borderline resectable or locally advanced pancreatic adenocarcinoma.
 

Number of Subjects	20 patients with pancreatic adenocarcinoma

Diagnosis and Main Inclusion and exclusion Criteria	
 
• Patients must be over 18 years old and capable and willing to provide informed consent
 
• Patients of childbearing potential must have a negative urine or serum pregnancy test within 7 days prior to PET/CT imaging per institution's standard of care
 
• Medically stable as judged by patient's physician
 
• Patients must have an ECOG performance status of 0-3 (restricted to ECOG PS 0-2 if age >70 years)
 
• Patients with known allergic or hypersensitivity reactions to previously administered radiopharmaceuticals of similar chemical or biologic composition to FLT are not eligible
 
• Patient must NOT be breast-feeding
 
• Histologically confirmed resectable, borderline resectable or locally advanced pancreatic adenocarcinoma 
 
• Patient have measurable disease (by RECIST 1.1 criteria)
 
 
 
• Patients with a history of prior therapy for pancreatic adenocarcinoma are NOT eligible 
 
• Patient must not weigh more than the maximum weight limit for the table for the PET/CT scanner (>200kg or 440lbs).
 
 
 
• Patient must be able to lie still for a 20 to 30 minutes for whole body PET/CT scan
 

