Study Product(s), Dose, Route, Regimen	Fluorothymidine is an analog of the nucleoside thymidine (deoxythymidine) but the 3'-F atom prevents FLT from following the full biochemical pathway of thymidine. FLT is transported from the blood into cells by active transport; it does not freely diffuse across the cell membrane. Once in the cell, FLT is a substrate for thymidine kinase I (TK1) and is phosphorylated but is not incorporated into DNA. 5mCi of FLT (+/- 20%) will be given intravenously.
Duration of administration	IV push over one to two minutes
Reference therapy	Not applicable

Statistical Methodology	
The difference in SUVmax, SUVpeak and proliferative tumor volume between baseline and post 2 cycles of chemotherapy will be correlated with overall survival at 1 and 2 years (primary clinical outcome endpoint) and progression free survival at 6 months and at 1 year (secondary clinical outcome endpoint) of patients with resectable, borderline resectable or locally advanced pancreatic adenocarcinoma using univariate and multiple cox regression model. Patient demographic information and tumor and treatment characteristics such as sex, race, tumor grade, cancer stage, last treatment modality, will also be included. P value less than 0.05 will be considered as statistical significant.
 
Areas under the ROC curve (AUC) and corresponding 95% confidence interval will be calculated for all models. Leave one out cross validation will be applied to avoid over-fit.

-------------------------	---

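### PFS is primary in 2.4 and 9.3 but secondary in 2.2 and the Study Summary, and no rule says how three PET parameters tested at an unadjusted P<0.05 decide the primary objective

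*Combined protocol and SAP*

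**What the plan says.** Section 9.3 describes the primary outcome variable in these words: "The difference in SUVmax, SUVpeak and proliferative tumor volume between baseline and 2 cycles of chemotherapy will be correlated with overall survival". The landmarks for OS are 1 year and 2 years. The same sentence adds PFS, with landmarks of 6 months and 1 year. Section 9.3 then restates the primary outcome as finding the degree of PET change that predicts OS and PFS together. The analysis is univariate and multiple Cox regression, and the decision rule is "P-value less than 0.05 will be considered as statistical significant". The secondary outcome in 9.3 is resectability: the same PET changes "will be correlated with binary tumor outcome measured from MRI/CT (resectable versus non-resectable disease) at 6 month using logistic regression".

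Other sections rank the outcomes differently. The Statistical Methodology row of the Study Summary puts OS first ("overall survival at 1 and 2 years (primary clinical outcome endpoint"). PFS carries the lower rank there ("progression free survival at 6 months and at 1 year (secondary clinical outcome endpoint"). Section 2.1 has OS alone as the primary objective and joins the three PET parameters with the word or. Section 2.2 has PFS as the secondary objective. Section 2.4 gives one primary endpoint, which ties a fall in the PET parameters to both longer PFS and longer OS. Section 2.3 lists no exploratory objectives.

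**The concern.** Two gaps combine. First, the rank of PFS depends on which section is read, so a study with a positive PFS result and a null OS result would meet the primary endpoint as 2.4 has it, yet fail the primary objective in 2.1. Second, even with OS alone there are three tests and no rule for a mixed result, such as SUVpeak below 0.05 and the other two parameters above it. The wording of 2.1 lets any one parameter answer the objective.

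What is at stake is an overstated claim that interim FLT PET/CT predicts survival. The documents do not tie treatment to the FLT result, so the harm lies in the conclusion and not in the care of participants.

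**Working it through.** **1. Rank of PFS, section by section**

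- Study Summary, Statistical Methodology row: secondary
- 2.2: secondary (2.1 has OS only)
- 2.4: primary, jointly with OS
- 9.3: primary, jointly with OS; the secondary outcome there is resectability, which 2.2 does not mention

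All four are current text and cannot all hold. This needs no calculation.

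**2. Does the sample size settle it?** Section 9.2 gives a difference of 0.124, SD 0.17, two-sided alpha 0.05 and 80% power. The normal approximation is n = ((1.960 + 0.842) × 0.17 / 0.124)² = 14.75, so 15, as the plan states. That calculation compares baseline with interim FLT SUV. It does not say SUVmax or SUVpeak, and it tests no association with survival, so it names no lead parameter or endpoint.

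**3. Reference values if the tests were independent.** The chance of at least one false positive among k tests at 0.05 is 1 − 0.95^k.

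- Three parameters on OS: 1 − 0.95³ = 14.3%
- Three parameters on OS and PFS: 1 − 0.95⁶ = 26.5%

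The parameters come from the same scans, and OS and PFS are related, so the true figures should be lower. With correlated normal test statistics and assumed correlations of 0.5 to 0.9, three tests give about 8–13% and six give about 12–22%.

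**4. Simulation of the Cox tests.** The documents give no PET correlations and no survival medians, so these inputs are assumptions:

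- n = 15 or 20 (section 9.2)
- three normal PET changes, unrelated to outcome
- correlations (SUVmax with SUVpeak, each SUV with volume) of (0.95, 0.3), (0.95, 0.6), (0.95, 0.9) and (0.8, 0.5)
- PFS exponential with median 6 to 18 months, analysed to 12 months
- OS equal to PFS plus an exponential time with median 6 to 20 months, analysed to 24 months
- univariate Cox score test, significant at |z| > 1.96, with 20,000 null datasets per setting

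Chance of at least one P<0.05:

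- one pre-specified test: about 5–6%
- three parameters on OS: about 9–14%
- three parameters on OS and PFS: about 15–23%

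**5. Small-sample part.** The single test slightly exceeds 5% because the score test is asymptotic. A wider grid of 60 settings also includes SUVmax–SUVpeak correlations of 0.3 and 0.6. On that grid, holding each single test at 5% moves the OS range from 8.7–16.4% to 7.8–14.1%, and the OS-plus-PFS range from 15.6–26.9% to 13.6–24.1%. Most of the excess over 5% is therefore multiplicity.

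The multiple Cox models, covariates and logistic model were not simulated, so these are not the exact error rates of the plan.

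**The case against.** The strongest reply is that this is a 20-patient, single-centre, non-randomised cohort whose title begins "Initial evaluation of role of early interim". One alpha-controlled test is a confirmatory standard, and full reporting of every estimate with its confidence interval would also be defensible. Much of this stands, and it is why a hypothesis-generating label is an acceptable remedy. But the plan does not apply that label: it sets a significance threshold for a primary outcome. The reply also leaves the contradiction on PFS untouched.

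A second reply is that the plan has a safeguard, namely AUCs with 95% confidence intervals and leave-one-out cross-validation. The Study Summary places these after the Cox models; 9.3 places them under the secondary outcome. They bear on over-fit and so give some protection against overstated prediction. They do not control error across parameters and endpoints.

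Some stronger readings are tempting but not supported:

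- *The investigators may pick the parameter and endpoint after seeing the data.* Section 9.3 commits to all three parameters and both outcomes, so showing only the favourable one would depart from the plan. What is missing is a rule for interpreting a mixed set.
- *The error rate is 21–38%.* That needs a separate Cox fit at every landmark (12 fits), which the plan does not state.
- *The error reaches 16% (OS) or 27% (with PFS).* Those values need a SUVmax–SUVpeak correlation of 0.3 to 0.6. Section 9.3 defines one as the hottest voxel and the other as the mean over 1 cubic cm in the hottest region, so so weak a relation is implausible.
- *Because 2.3 lists nothing, the tests are confirmatory.* It shows only that no further objectives were listed.

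**Conclusion.** The point holds and should be corrected. The contradiction on PFS is certain from the text. So is the absence of a lead parameter, test order or adjustment, which leaves the primary objective without a decision rule when results are mixed.

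The size is less certain. The fairer headline is about 9–14% for three parameters on OS, since 2.1 and the Study Summary rank OS first. It rises to about 15–23% if PFS is also primary. Both ranges rest on assumed SUVmax–SUVpeak correlations of 0.8 to 0.95 and on assumed survival medians.

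**What to change.** 1. Make PFS secondary in 2.4 and 9.3, in line with 2.2 and the Statistical Methodology row.
2. Before any outcome analysis, name one primary test in 2.4, the Statistical Methodology row and 9.3: percentage change in one pre-specified PET parameter, in a univariate Cox model for OS as a time-to-event variable, two-sided 0.05.
3. State the time origin for OS, which the documents do not define. It should be no earlier than the interim scan, because percentage change is unknown before then; OS counted from the interim scan would serve. State the end of follow-up too, since 4.0 gives 24 months and 4.1 gives up to 2 years after chemotherapy ends.
4. Report the other parameters and PFS as estimates with 95% confidence intervals, or Holm-adjusted.
5. If outcomes have already been examined, or the sponsor prefers no lead parameter, label all association results hypothesis-generating.
6. As wording alignment only, use percentage change throughout (the Study Summary objective already reads "To assess if percentage change in", while 9.3 speaks of a difference and 2.4 of a decrease), and add resectability to 2.2.

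Cost: a protocol amendment with IRB approval under 10.8, with no new patients or data. The other parameters could no longer be claimed at an unadjusted 0.05. The page footer in section 5.1 is dated 08-19-20, and the documents do not say whether outcomes have been examined. If they have, an amendment cannot restore pre-specification, and only the label in item 5 remains for the association tests.

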## 1.0 BACKGROUND AND RATIONALE

### 1.1 Disease Background

Pancreatic cancer is the fourth most lethal malignancy overall, with a projected death toll of more than 40,000 for 2016 in the US. Pancreatic adenocarcinoma is usually locally advanced and / or metastatic at the time of diagnosis, preventing surgical resection in the majority of cases. Initial treatment strategies for resectable, borderline resectable or locally advanced pancreatic adenocarcinoma includes chemotherapy and chemoradiation (in selected patients). The main therapeutic goal is to reduce disease burden to allow surgical resection, which is the only curative treatment for pancreatic adenocarcinoma to date. After initial treatment, response is reevaluated by anatomical imaging, usually by a dedicated contrast enhanced CT, which is preferred, or alternatively MRI. However, objective evaluation of response in pancreatic cancer is often difficult. CT and MRI have some significant limitations, such as inability to clearly outline tumor borders due to the infiltrative nature of pancreatic adenocarcinomas, and post-treatment imaging changes that can simulate tumor. Additionally, it is an anatomic method only that relies on relatively slow macroscopic tumor changes without information regarding tumor metabolism.

2-Deoxy-2-[F]-fluoro-D-glucose (F-FDG) PET/CT, which is a marker of glucose metabolism, is an alternative imaging method, and multiple studies have shown an overall sensitivity of 73 to 94% for detection of pancreatic adenocarcinoma, while specificity ranges from 60 to 89%. The specificity is reduced because F-FDG PET/CT is a non-specific tracer that also accumulates in some benign conditions with increased glucose metabolism (such as inflammation). Moreover, the rate of false negatives is also

increased in this population because 20 to 30% of patients with pancreatic adenocarcinoma have hyperglycemia, which may significantly decrease the amount of FDG uptake. For these reasons, more accurate novel PET tracers are expected to have a significant clinical impact.

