### **1.4 Rationale**

The thymidine analog 3'-deoxy-3''[F]-fluorothymidine (FLT) is a proliferation marker, which has the potential to perform better in patients with pancreatic adenocarcinoma.

Interim studies (usually after 2 cycles of chemotherapy) are commonly used for early restaging and to better tailor further management, offering more timely evidence to support changing or maintaining therapies, when compared to conventional imaging studies. It also has an important role in prognostication. Such study strategies have been extensively explored for breast cancer, and at least three different studies showed significant correlation between findings in early F-FLT PET/CT and patients' response to chemotherapy, giving the possibility of change in chemotherapy regimens in non-responder patients.

The increased specificity of F-FLT PET/CT has an enormous advantage over F-FDG PET/CT as an early assessment study, especially with radiation therapy. F-FDG PET/CT is known to suffer from an increased rate of false positives due to non-specific uptake in post-therapy inflammatory changes during treatment caused by macrophage / monocyte infiltration. F-FLT PET/CT has the potential to overcome this limitation as a more specific tracer for tumor proliferation.

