## **4.0 STUDY PLAN**

N.B: FDG PET/CT can be performed before or after baseline FLT, but must be within 30days of baseline PET/CT.

The experimental  $^{18}\text{F}$ -FLT-PET/CT is required to be completed before initiation of chemotherapy. Labs and correlative radiology, as directed per clinical care, are required within 30 days prior to  $^{18}\text{F}$ -FLT-PET/CT; and optional  $^{18}\text{F}$ -FDG-PET/CT within 30 days of the  $^{18}\text{F}$ -FLT-PET/CT. Follow-up will comprise 24 months of standard practice treatment and follow up.

**Visit 1:** Patients will have at least one visit with investigator (or investigator designee) prior to the study to review clinical history and prior treatment of pancreatic adenocarcinoma, and to explain the study. Correlative radiology studies including CT, MRI and/or  $^{18}\text{F}$  FDG-PET/CT as per institutional routine clinical care, and any clinically-directed laboratory tests performed as part of staging. All clinical care tests must be performed within 30 days of the  $^{18}\text{F}$  FLT-PET/CT. The following additional patient data will be obtained: histological diagnosis of primary and/or metastatic disease, date of diagnosis of primary and no evidence of metastatic disease, gender, height, weight (for BMI), ECOG score and confirmation of absence of prior treatment.

**Visit 2(optional):** The  $^{18}\text{F}$ -FDG-PET/CT may be done as a research scan if patients agrees to that, if the patient is unable to obtain a clinically-directed  $^{18}\text{F}$ -FDG-PET/CT as part of their clinical care or within 30 days of  $^{18}\text{F}$  FLT-PET/CT, before or after the baseline FLT. The research  $^{18}\text{F}$ -FDG-PET/CT, in this instance, will be identical in procedure to the institution's clinical  $^{18}\text{F}$ -FDG-PET/CT. The blood glucose level will be  $< 200$  mg/dl, before  $^{18}\text{F}$ -FDG injection, which is institutional standard clinical protocol.

---

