**Visit 3:** Day of F-FLT-PET/CT: The patient will have an intravenous line placed in the hand or arm, F-FLT-PET/CT will be given by 1-2 minute IV push, and the dose administered will be approximately 5 mCi (+/- 20% dose). After approximately 60 +/- 10 minutes of uptake time, the patient will be positioned supine in the PET/CT scanner for standard whole body PET/CT scan from the skull base to mid-thigh. This scan will take approximately 20-30 min. The window from FLT PET/CT baseline study to initiation of chemotherapy should be no more than 30 days.

**Visit 4:** Day of Interim F-FLT-PET/CT: The interim F FLT-PET/CT will be performed after the 2nd cycle of chemotherapy regimen, but before the commencement of 3rd cycle. The second F-FLT-PET/CT study must be performed on the same scanner as the first F FLT-PET/CT and the imaging protocol described in Visit 3 should be closely followed.

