## **9.0 STATISTICAL CONSIDERATIONS**

### **9.1 Study Design/Study Endpoints**

We anticipate to enroll 20 patients with biopsy proven pancreatic adenocarcinoma that are not eligible for resection by the time of the diagnosis. These patients are going to be treated with chemotherapy only or chemoradiation in selected cases. These patients will undergo an optional F FDG PET/CT (as standard of care clinical baseline) and F-FLT PET/CT before treatment (research baseline study), and after two cycles of chemotherapy (research early therapy assessment study).

For the F-FLT PET/CT analysis, SUV max, SUV peak and proliferative tumor volume will be measured by MIMvista software and compared between the two studies. Tumor size and extension will also be evaluated on CT images from the PET/CT study.

At completion of treatment (6 months after baseline FLT PET/CT) an anatomic study (MRI or CT) will be performed as standard of care in our institution to reassess the tumor and classify it as resectable or non-resectable. Also at 6 months, 1 year and 2 years after initial baseline scan, or before if clinically indicated, standard of care anatomic study (MRI or CT) will also be performed and will be reevaluated by RECIST criteria to determine stability versus progression of disease.

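### The plan does not keep the interim FLT result from those who judge resectability and progression, so reader knowledge can inflate both associations

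*Combined protocol and SAP*

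**What the plan says.** **Predictor.** Section 4.0 (Visit 4) places the interim FLT scan after the second cycle of the "chemotherapy regimen, but before the commencement of" the third. Section 9.1 describes both FLT scans as research studies. It also has tumor size and extent read on the CT part of the FLT PET/CT.

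**Resectability.** Section 9.1 has a CT or MRI at completion of treatment, 6 months after the baseline FLT scan, "performed as standard of care in our institution to reassess the tumor and classify it as resectable or non-resectable". In 9.3 this call is the secondary outcome variable: a "binary tumor outcome measured from MRI/CT (resectable versus non-resectable disease) at 6 month using logistic regression".

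**Progression.** Section 9.1 says that at 6 months, 1 year and 2 years, "or before if clinically indicated, standard of care anatomic study (MRI or CT) will also be performed", and that it "will be reevaluated by RECIST criteria to determine stability versus progression of disease". PFS at 6 months and 1 year rests on these reads (6.1). PFS is part of the primary endpoint in 2.4 and of the primary outcome variable in 9.3. Section 2.2 and the Study Summary make it secondary.

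**Reliability of the reads.** Among the limitations of CT and MRI, section 1.1 lists "inability to clearly outline tumor borders due to the infiltrative nature of pancreatic adenocarcinomas" and post-treatment changes that resemble tumor.

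**Treatment after the scan.** Section 4.0 states: "Follow-up will comprise 24 months of standard practice treatment and follow up". Section 9.1 allows chemoradiation in selected patients.

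**The concern.** A study of whether a marker predicts an outcome needs the outcome to be judged independently of the marker. Here the marker is known first, the outcome is partly a matter of opinion, and the plan names neither the reader nor what the reader may see. A reader who knows that FLT uptake fell may lean towards resectable or stable in a borderline case. One who knows that it rose may lean the other way. Both produce the association the study is looking for, with no biological link behind it.

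Scan timing is a second route. PFS runs to the time of progression (6.4.5). An unscheduled CT prompted by a poor FLT result can therefore find progression sooner and shorten the recorded PFS.

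At stake is whether an observed association with resectability or PFS can be read as predictive information in the FLT change.

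**Working it through.** **1. Is there a barrier anywhere?** The available text was read in full for blinding, masking, independent or central reading, or withholding of FLT results. None was found in the visit descriptions (4.0), the time and events table (5.2), the measurement section (6.0), the statistical section (9.0) or the data management section (10.4). The schema figure and consent pages are not available, so the finding covers the remaining text only.

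**2. Does the marker come before the outcome?** Yes. FLT is acquired before cycle 3. The resectability call is at 6 months, and the RECIST reads are at the end of chemotherapy and in follow-up.

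**3. Which outcomes can the FLT result reach, and in which direction?**

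| Outcome | Through the reader | Through scan timing | Through treatment or surgery |
|---|---|---|---|
| Resectability | Yes, inflates | Little: fixed at 6 months | Yes, either direction |
| PFS | Yes, inflates; limited by numeric thresholds | Yes; inflates if poor FLT prompts the scan | Yes, either direction |
| Overall survival | No: death is not a reading | No | Yes, either direction |

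The treatment column has no fixed sign. Changing therapy in FLT non-responders could weaken the association, while not offering them surgery would strengthen it.

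**4. How large could the reader effect be?** The plan gives no figure on this point to reproduce. Every input below is assumed, except the numbers of patients (15 and 20), which come from 9.2.

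*Odds ratio.* Assume no true association, 50% resectable, FLT split into improved or not, and knowledge of FLT moving the call by s each way. Then OR = [(0.50 + s)/(0.50 − s)]².

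- s = 0.05: (0.55/0.45)² = 1.49
- s = 0.10: (0.60/0.40)² = 2.25
- s = 0.15: (0.65/0.35)² = 3.45

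*False-positive rate.* Keep FLT change continuous with no true association. Let a share q of resectability calls simply follow FLT. Resectable prevalence is 30% or 50%, n is 15 or 20, with 20,000 simulations per setting and a two-sided 5% rank test in place of the planned logistic regression. At 50% prevalence, the chance of a resectable call in the improved half is q + (1 − q) × 0.5 = 0.5 + q/2, so s = q/2.

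| q | Matching s | Mean apparent AUC | Rejection rate over the four settings |
|---|---|---|---|
| 0% | 0 | 0.50 | 4.6% to 5.0% |
| 10% | 0.05 | 0.55 | 5.9% to 6.7% |
| 20% | 0.10 | 0.60 | 8.8% to 11.0% |
| 30% | 0.15 | 0.65 | 13.7% to 19.9% |

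The odds ratios look more dramatic than the test behaves. With 15 to 20 patients, a 5-point shift barely moves the false-positive rate, and a 10-point shift roughly doubles it. The AUC estimate is biased throughout.

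**5. Does the planned validation help?** No. Leave-one-out cross-validation (9.3) guards against over-fitting. Each left-out patient's outcome carries the same reader influence, so the validation would reproduce the bias.

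**The case against.** The strongest reply is that the primary objective (2.1) is overall survival, which no reader can misclassify. Resectability is absent from the objectives in 2.1 to 2.3, and RECIST applies numeric thresholds (6.4.1). Most of this stands, and it limits the point to resectability and PFS. It does not remove the point: PFS is in the endpoint statement of 2.4 and the primary outcome variable of 9.3, and new or non-target lesions (6.4.2) still need judgement.

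A reader might infer from 1.4 that FLT is meant to steer treatment, since it describes interim studies as "offering more timely evidence to support changing or maintaining therapies". The documents do not support that. The sentence is general background, and the remark on changing regimens concerns breast cancer. No visit or procedure sends the FLT result to the treating team. Equally, calling the scans research and follow-up standard practice does not say that anyone is kept from seeing them.

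A reader might also infer that the bias must favor the hypothesis, or that it could never be undone. Neither follows. Bias through treatment can go either way, and an early scan prompted by an FLT improvement would work against the hypothesis. Archived CT/MRI can be re-read by someone unaware of FLT. Only effects through treatment and scan timing cannot be recovered.

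Finally, the shifts in the illustration have no source in the documents. That is correct, and they should be read only as a scale.

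**Conclusion.** The point holds for resectability and PFS. The available text leaves both open to reader knowledge of the FLT result, which would inflate the association, and the planned cross-validation cannot detect or remove this. Overall survival is exposed only indirectly, with no fixed direction. The documents show that influence is possible, not that it occurred.

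The size is unknown. Under the assumptions in the working, a 5- or 10-point shift each way gives an odds ratio of about 1.5 or 2.25 where none exists. No figure can be given for PFS or overall survival, because the plan states no event rates. The change should be made because it is cheap and protects outcomes the plan intends to report. The sample size is unaffected.

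**What to change.** **In 9.1 and 9.3:** state that the resectability call and every RECIST read used for PFS, through the 1-year read, are made and locked in REDCap without access to FLT images or values. The existing standard-of-care CT/MRI readers can do this. If one person handles both, FLT review and quantification can wait until that patient's reads are locked. No extra reader is needed.

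**In 4.0 (Visit 4):** state who may see the interim FLT result. Record whether it was known at each treatment change, surgical decision or unscheduled scan, so that this can be reported and examined in a sensitivity analysis. This covers the treatment and timing routes that blind reading cannot close.

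**For patients already assessed:** any outcome read with FLT known should be re-read blind from the archived scans, or the exposure disclosed.

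**Cost:** protocol wording, a data-entry lock and a few extra fields. FLT quantification or release comes later, by up to the time of the 1-year read where one person does both. No scan or patient is added, and no rule on treatment is proposed.
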